9.4.2 ANALYSIS OF THE PRIMARY EFFICACY OUTCOMES(S)

The primary outcome will be the mean change in dysphagia as measured by the EEsAI score (7-day recall) from baseline to 3-months post-treatment. Patients will complete this measure at screening (baseline), and then every month throughout the study when they come for their medication injection. This study will consider baseline at the point when symptoms are assessed prior to the study drug being given.

We are focusing on symptoms as the primary outcome as this is the key clinical metric for a PRO-measured treatment response.⁴¹ The EEsAI is a validated and responsive PRO, developed by an international team of EoE experts, that measures dysphagia frequency, dysphagia severity, and food avoidance/modification behaviors, in patients with EoE.^{42, 45-47} It has now been used in several clinical trials, including recently published abstract data emphasizing the responsive nature of this instrument.⁴⁸ In the first, 59 subjects were randomized to receive an or disperisble budesonide tablet and 29 to placebo.⁵¹ A total of 30 patients (59%) in the active arm achieved an EEsAI score of ≤ 20 compared to just 2 patients (7%) in the placebo arm ($p < 0.0001$). In the second study, which was a study of the anti-IL-4 α receptor blocker dupilumab, EEsAI was measured in a subset of patients had EEsAI.⁴⁹ The 17 patients who received active treatment had a 36% decrease in the EEsAI score compared to an 11% decrease in the 13 patients who received placebo ($p = 0.085$). These new data support the use of the EEsAI as a primary outcome. The EEsAI score can range from 0 to 100, with higher scores indicated more severe symptoms; a decrease of 20 points is felt to be a meaningful clinical response, and scores ≤ 20 represent clinical remission.

For the primary outcome, the mean change in dysphagia from baseline to 3-months post-treatment (as measured by the EEsAI score with 7-day recall) will be compared between the mepolizumab and placebo groups using analysis of covariance. In discussion with the study statistician, the main factor that we will include in the primary analysis is the baseline EEsAI score, though in the exploratory analyses we will assess trial site. We will also include the stratification factor (prior steroid response as a covariate as appropriate in the analyses (see below as well).

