6.3 MEASURES TO MINIMIZE BIAS: RANDOMIZATION AND BLINDING

Subjects will be randomized 1:1 to either mepolizumab or a placebo injection. Randomization will be administered centrally but will be at the level of the site using a blocked randomization protocol with computer-generated variable block sizes. At each site, patients will be categorized as either a prior steroid non-responder or not, and then will be randomized within that categorization. The investigational pharmacy at each site will then receive the randomization information and provide study drugs. Allocation will be concealed from all investigators, subjects, and data analysts. The study monitor will be unblinded to treatment assignments and can escalate issues to the medical monitor who can be unblinded if necessary (e.g. in the event of a safety concern or DSMB request). Of note, we will balance the groups for prior steroid non-response but will not be formally stratifying on this variable for power calculations or analysis purposes. Steroid non-response is defined as greater than 15 eos/hpf after a 2-month course of a swallowed/topical steroid at a standard dose (standard dose = 2mg/d of budesonide or 1760 mcg/d of fluticasone).

This is a double-blind study. Subjects, investigators, endoscopists, nurses, statisticians, and study staff will all be masked as to allocation. To maintain the study blind, only unblinded pharmacist(s) at the investigational pharmacy at each site will dispense study drug. The medication will be mixed by the investigational pharmacy, and only blinded syringes with "study drug" will be provided to use in the study. These will either have the correct active dose of mepolizumab or a matched normal saline placebo. In the first blinded phase, subjects randomized to mepolizumab will receive three injections with active medication, and subjects randomized to placebo will receive three injections with placebo. In the second blinded phase, subjects who were initially randomized to mepolizumab will continue to receive three injections of active medication. However, subjects who were initially randomized to placebo will receive one injection of mepolizumab and 2 injections of placebo.

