9.4 STATISTICAL ANALYSES

9.4.1 GENERAL APPROACH

Descriptive statistics will be used to describe the data. Categorical variables will be presented as proportions and means will be presented with standard deviation and range. If the data are not normally distributed, medians and interquartile ranges will be presented rather than means, and non-parametric testing will be used. For inferential tests, a p value < 0.05 will be considered significant and all tests will be two tailed. All statistical estimates (e.g., medians, proportions, incidence rates, mean differences, correlations, etc.) will be tabulated along with corresponding confidence intervals (CIs).

Interpretation of CIs will play a major role as an integral part of the analysis of the data in concert with any statistical hypothesis tests. To avoid over-reliance on p-values, the magnitudes of estimates and the corresponding confidence intervals will be a focus of the analyses. Reasons for missing data will be investigated and recorded for purposes of statistical analyses. Because of the study design and outcome assessment, primary analyses will require exclusion of participants without outcome data. However, we will perform sensitivity analyses for missing data, initially assigning participants lost to follow up to treatment failure, then assigning them to treatment success and comparing the results, a technique that has been successful in prior clinical trials conducted by our group. For all outcomes, the null hypothesis is that there is no difference between the study groups. All hypothesis tests that are observed to be NOT statistically significant will be reported as being inconclusive.

The study statistician on this study will be [name].

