- Response outcomes (noted above) in prior steroid responders vs. non-responders. Steroid non-response is defined as greater than 15 eos/hpf after a 2-month course of a swallowed/topical steroid at a standard dose (standard dose = 2mg/d of budesonide or 1760 mcg/d of fluticasone). Of note, the randomization is balanced for prior steroid response, but the study is not powered for this exploratory outcome. We will also explore the response outcomes in the context of all prior EoE treatments to understand heterogeneity of treatment response, if present, and will include this stratification factor as a covariate in the above analyses, as appropriate.
- Response outcomes (as noted above) in patients on a restrictive diet vs. an inclusive diet. A restrictive diet will be defined as any diet at baseline (which also must be maintained through the study) that is either limited in foods because of EoE or because of food allergies/intolerances.

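### The primary ANCOVA omits site and does not firmly include prior steroid non-response, although randomisation is blocked within both

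*Combined protocol and SAP*

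**What the plan says.** On randomisation, Section 6.3 states: "Randomization will be administered centrally but will be at the level of the site using a blocked randomization protocol". It continues: "At each site, patients will be categorized as either a prior steroid non-responder or not, and then will be randomized within that categorization". The synopsis (Section 1.1) gives four US sites enrolling competitively, so there are 4 × 2 = 8 strata.

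On analysis, Section 9.4.2 states: "main factor that we will include in the primary analysis is the baseline EEsAI score, though in the exploratory analyses we will assess trial site". It then says of steroid response: "We will also include the stratification factor (prior steroid response as a covariate as appropriate in the analyses". Section 9.4.9 repeats that the analysts "will include this stratification factor as a covariate in the above analyses, as appropriate". Neither section says what would make inclusion appropriate. Section 6.3 says of the same variable that the trial "will not be formally stratifying on this variable for power calculations or analysis purposes".

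**The concern.** The primary analysis does not carry the grouping that the design imposes. There are two parts.

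- **Site.** Leaving it to exploratory analyses is a stated choice and is not ambiguous.
- **Steroid response.** The text is unclear. Section 6.3 appears to rule the factor out of the analysis, while Sections 9.4.2 and 9.4.9 call it the stratification factor and a conditional covariate. One reading reconciles them: baseline EEsAI alone in the primary model, with steroid response entering only in the Section 9.4.9 analyses. The plan does not say so, and a second statistician could not write down the primary model from it.

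At stake is the calibration of the primary interval. If the blocked factors predict EEsAI change, the treatment estimate varies less from trial to trial than a model omitting them reports. Section 9.4.1 says that "the magnitudes of estimates and the corresponding confidence intervals will be a focus of the analyses", and it treats every non-significant test as inconclusive, so unnecessary width bears directly on how the result will be read.

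**Working it through.** **Plan's own figure.** From Section 9.2: difference 17, SD 20, two-sided α 0.05, power 0.90. The two-sample normal formula gives n = 2 × 20² × (1.960 + 1.282)² / 17² = 800 × 10.51 / 289 = 29.1, rounded up to 30 per group, as stated. All ten table rows reproduce this way. The calculation has no covariate or stratum term.

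**Inputs.** From the plan: SD 20, 72 randomised, 60 evaluable, four sites, 1:1 allocation in variable blocks. Assumed, because the documents give no values:
- correlation of baseline EEsAI with change, 0.4 (range 0.2 to 0.6);
- 40% steroid non-responders;
- site and steroid response together explaining 0, 10 or 20% of total variance, split equally.

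**Closed form at correlation 0.4.** Baseline leaves 1 − 0.4² = 0.84 of the variance. The full model leaves 0.84 − 0.10 = 0.74 or 0.84 − 0.20 = 0.64. With SE ≈ 20 × √(share left) × √(2/30):
- baseline only: 20 × √0.84 × 0.258 = 4.73;
- full model, 10% share: 20 × √0.74 × 0.258 = 4.44;
- full model, 20% share: 20 × √0.64 × 0.258 = 4.13.

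The ratios are √(0.84/0.74) = 1.065 and √(0.84/0.64) = 1.146, before the loss of degrees of freedom.

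**Simulation.** 60 scenarios of 4,000 trials each, with permuted blocks (2/4 or 4/6) in the 8 strata, sites equal or 50/25/15/10, and 12 of 72 patients dropped at random. Residual degrees of freedom are 57 for baseline only and 53 for the full model. Ranges at correlation 0.4:

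| Joint share | Model | Mean reported SE | Actual SD of estimate | 95% CI half-width |
|---|---|---|---|---|
| 10% | Baseline only | 4.76–4.78 | 4.59–4.69 | 9.5–9.6 |
| 10% | Full | 4.50–4.53 | 4.54–4.65 | 9.0–9.1 |
| 20% | Baseline only | 4.76–4.78 | 4.32–4.43 | 9.5–9.6 |
| 20% | Full | 4.19–4.22 | 4.18–4.30 | 8.4–8.5 |

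- **SE excess from omitting both:** 5 to 6% (10% share) and 13 to 14% (20% share). If steroid response is in and only site is out, it is 2.3 to 2.7% and 6.5 to 6.8%.
- **Type I error, baseline only:** 0.040 to 0.046 and 0.028 to 0.036. The full model gives 0.046 to 0.056. Monte Carlo error is about 0.003.
- **Other correlations (0.2 to 0.6):** SE excess 4.5 to 8% and 11 to 20%. If the share is instead taken of the variance left after baseline, 4 to 5% and 10.5 to 11%.
- **Power at 17 points, baseline only:** 0.904 to 0.991 in all 60 scenarios. At correlation 0.4 the full model adds 1.0 to 1.7 points (10% share) and 2.1 to 3.1 points (20% share).
- **Neither factor prognostic:** SE rises from 4.76–4.77 to 4.81–4.83.

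**Repeat checks.** Further runs at correlation 0.4 gave the same SEs to within 0.01. Baseline-only type I error was somewhat lower, at 0.032 to 0.040 (10%) and 0.027 to 0.032 (20%). A run with baseline not prognostic and site shares of 40/25/20/15 gave baseline-only type I error of 0.046, 0.039, 0.030 and 0.022 at joint shares of 0, 10, 20 and 30%, against 0.047 to 0.050 for the full model. Full CI width was 20.8 points throughout for baseline only, against 20.9, 19.8, 18.7 and 17.5 for the full model.

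**The case against.** The strongest reply is about weight. Leaving site out was decided with the study statistician and disclosed. Section 9.4.2 calls baseline EEsAI the main factor, not the only one, so steroid response may well be in the model, which roughly halves the loss. Nothing in the documents shows that either factor is prognostic, and a 20% joint share is only an assumption. Most of the gain is better calibration rather than real precision: the actual SD of the estimate falls only about 1% (10% share) or 3% (20% share).

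Nor does the open wording invite false positives. Picking the smaller p-value with or without steroid response gave type I error of 0.033 to 0.048, and the best of four models gave 0.051 to 0.057. Section 6.3 also masks the analysts: "Allocation will be concealed from all investigators, subjects, and data analysts". Finally, pooling small sites could erode the benefit.

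All of this stands as a limit on severity, except most of the pooling point. Merging a site with fewer than 5 patients left the figures essentially unchanged. Only coarse pooling to two groups matters, cutting the SE excess to about 4% and 9 to 10%. The reply does not remove the mismatch between design and model, or supply the missing criterion for steroid response.

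**Conclusion.** The concern holds and the change should be made, though it does not threaten the trial's validity. With only baseline EEsAI in the model, the reported interval is too wide and the test conservative whenever site or steroid response predicts EEsAI change. The standard error excess is 5 to 6% at an assumed 10% joint share and 13 to 14% at 20%, with an assumed baseline correlation of 0.4. There is no bias, no excess of false positives and no loss of planned power at 17 points. If neither factor is prognostic, omission costs nothing. Confidence is high on the gap in the text and the direction of the effect. The size depends on the stated assumptions.

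**What to change.** In Section 9.4.2, fix one covariate set for the primary ANCOVA: treatment, baseline EEsAI, prior steroid non-response and site, as main effects. Remove the conditional wording on steroid response for that model, and reconcile the Section 6.3 clause on analysis with it. Use the same factors in the EREFS and SDI ANCOVAs of Section 9.4.3, each with its own baseline. The chi-square and t-test comparisons there can stay unadjusted.

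Add a rule for pooling small sites, fixed before unblinding. Enrolment is competitive: with sites at 50/25/15/10, the smallest had fewer than 5 evaluable patients in 29 to 32% of simulated trials, against at most 0.2% with equal sites. Keep pooling to the minimum needed.

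The cost is wording and four degrees of freedom (57 to 53). If neither factor matters, the standard error rises 0.9 to 1.3% and power at 17 points falls by 0 to 1.2 points over correlations of 0.2 to 0.6. If the sponsor prefers baseline EEsAI alone, the plan should say so outright and accept a conservative interval.

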9.4.3 ANALYSIS OF THE SECONDARY OUTCOMES(S)

Secondary outcomes are as follows:

- The proportion of patients who have clinical remission as defined by an EEsAI score of ≤ 20 . This will be compared between groups by chi-square.

- The proportion of patient who have a clinical response, as defined by an EEsAI score decrease of ≥ 20 points. This will be compared between groups by chi-square.
- The absolute peak eosinophil count (measured in eos/hpf) after 3-months of treatment. Eosinophil counts will be measured by our previously validated protocol, with central reading of all biopsy samples at the lead site to ensure a consistent reading approach.⁴⁹ This will be compared between groups with a two-sample t-test.
- Levels of histologic response after 3-months of treatment including < 15 , ≤ 6 , and ≤ 1 eos/hpf. This will be compared between groups by chi-square.
- Mean change in severity of endoscopic findings as measured by the EoE Endoscopic Reference Score (EREFS) from baseline to 3-months post-treatment. EREFS is a validated and responsive endoscopic severity score that assesses the five most common endoscopic features of EoE: exudates, rings, edema, furrows, and strictures.^{50, 51} This will be compared between the groups using analysis of covariance.
- Mean change in the Straumann Dysphagia Instrument (SDI) from baseline to 3-months post-treatment. The SDI is a direct measure of dysphagia frequency and severity with a 7-day recall period. The score ranges from 0-9, with higher scores indicating more severe dysphagia. This instrument, while not validated, has been shown to be responsive in at least 2 clinical trials.^{23, 49} This will be compared between the groups using analysis of covariance.

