5 STUDY POPULATION

5.1 INCLUSION CRITERIA

In order to be eligible to participate in this study, an individual must meet all of the following criteria:

1. Age 16-75*
2. Diagnosis of EoE as per consensus guidelines (including PPI non-response**).^{2, 43}
3. Active eosinophilia on esophageal biopsy, with a peak count of least 15 eos/hpf from at least one esophageal level.***
4. Biopsies from the stomach and duodenum that have ruled out alternative etiologies in all children and in adults with abnormal endoscopic findings or when other gastric or small intestinal conditions are clinical possibilities. If these samples have been obtained during a previous endoscopic evaluation and in the judgement of the site-Investigator the patient has not had a clinically significant change that would merit repeat gastric/duodenal biopsies, then prior normal gastric and duodenal biopsies are acceptable to exclude alternate etiologies.
5. Active symptoms of dysphagia with more than 3 episodes of dysphagia over a period of 2 weeks during the screening period, and an Eosinophilic Esophagitis Symptom Activity Index (EEsAI; see below for details) score of ≥ 27 at baseline.****
6. Able to read, comprehend, and sign consent form.
7. Have maintained a stable diet for 6 weeks prior to enrollment.*****
8. Able to maintain a stable diet throughout the duration of the study period. *****
9. Female subjects of childbearing potential who have had their first menses agree to use a highly effective method of birth control during the study and for 30 days after the last dose of study drug. Female subjects with reproductive potential who are using systemic contraceptives (e.g., oral contraceptives, injectable contraceptives, implantable/insertable hormonal contraceptive products, or transdermal patches) to prevent pregnancy must have stable use for ≥ 28 days prior to screening. See section 5.3 for additional details.

* The rationale for this criterion is that adolescents and adults with EoE have a very similar clinical presentation with dysphagia-predominant symptoms.²¹ If we were to enroll younger patients there would be few who would meet the dysphagia threshold, and the symptom metric we will use was not validated in younger patients.⁴² Patients of any age can have EoE, but in patients above the age of 75 malignancy is a concern with clinical symptoms of dysphagia, and EoE becomes less common.¹²

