9.2 SAMPLE SIZE DETERMINATION

The study is powered for the primary outcome, the EEsAI score, which can range from 0-100, with a score of ≤ 20 indicating clinical remission, and a decrease of ≥ 20 points indicating a meaningful clinical response. Based on this, we estimate that with a sample size of 30 patients in each group we would be able to detect a difference in the mean change in EEsAI score of as little of 17, with a power of 0.9 at an α of 0.05, which would allow us to detect the clinically meaningful difference of 20 (see Table). Assuming a 20% dropout rate, we plan to randomize 36 patients in each group.

Table: Sample size considerations

Estimated mean decrease in EEsAI score after 12 weeks of treatment*				
Placebo	Mepolizumab	α	Power	N per group
10	30	0.05	0.9	22
15	30	0.05	0.9	38
20	30	0.05	0.9	85
10	35	0.05	0.9	14
15	35	0.05	0.9	22
15	32	0.05	0.9	30
20	35	0.05	0.9	38
10	40	0.05	0.9	10
15	40	0.05	0.9	14
20	40	0.05	0.9	22

*SD 20 for all

For the secondary outcome of proportion of patients with an EEsAI score ≤ 20 indicating clinical remission, a sample size of 30 in each group would allow us to detect as little as a 40% difference in remission rates between placebo and active therapy with a power of 0.9, a smaller difference that was detected in a recent trial using this metric.⁴⁸ This sample size would also provide ample power the for the absolute eosinophil count and EREFS secondary outcomes.

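### Clinical remission and response are tested by unadjusted chi-square; adjusting for baseline EEsAI, already in the primary model, would be a cheap and modest gain in precision

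*Combined protocol and SAP*

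**What the plan says.** Section 9.4.3 lists two binary outcomes first among the secondary outcomes. The first is "clinical remission as defined by an EEsAI score of ≤ 20 . This will be compared between groups by chi-square". The second is response, "as defined by an EEsAI score decrease of ≥ 20 points. This will be compared between groups by chi-square". Neither entry names a covariate. The same section uses analysis of covariance for the change scores on EREFS and SDI.

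Section 9.4.2 analyses the change in EEsAI by analysis of covariance and says that "the main factor that we will include in the primary analysis is the baseline EEsAI score". On collection it says: "Patients will complete this measure at screening (baseline), and then every month throughout the study".

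The other covariate wording concerns prior steroid response. Section 9.4.2 mentions it as a possible covariate, and section 9.4.9 says the investigators "will include this stratification factor as a covariate in the above analyses, as appropriate". Neither place brings baseline EEsAI into the remission or response comparison. Section 6.3 randomises within site and prior steroid non-response, so the design does not balance baseline EEsAI either.

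Section 5.1 requires an EEsAI "score of ≥ 27 at baseline", and its notes expect typical baseline scores of 50 to 60. Section 9.4.1 sets the test level: "a p value < 0.05 will be considered significant and all tests will be two tailed".

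**The concern.** The starting score affects both binary outcomes by definition. A patient entering at 70 is a responder on reaching 50, but needs a 50-point fall for remission. A patient entering at 27, the lowest permitted score, needs only a 7-point fall for remission but must reach 7 or below to respond.

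If month-3 and baseline scores are positively related with a slope below 1, a higher baseline raises the chance of response and lowers the chance of remission. An analysis that ignores a known predictor of the outcome gives up some precision, and here the predictor is already in the database and in the primary model.

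What is at stake is the precision of the two secondary results most likely to be read beside the primary one. The validity of those results is not in question.

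**Working it through.** **1. The plan's own figures.** Section 9.2 gives 30 per group for a "difference in the mean change in EEsAI score of as little of 17, with a power of 0.9 at an α of 0.05", with SD 20.

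- n = 2(1.960 + 1.282)² × 20² / 17² = 29.1, rounded up to 30. Power at 30 is 90.9%. All ten rows of the sample-size table reproduce.
- For a 40-point remission difference at 30 per arm, by uncorrected chi-square, the placebo rate is not stated. Power is 95.7% for 7% vs 47%, 90.6% for 20% vs 60%, and 89.3% for 30% vs 70%. The stated 0.9 is therefore sound without adjustment.

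**2. Response by chi-square at the plan's detectable difference.** Assume normal changes with SD 20 and mean falls of 15 and 32 (a row of the plan's table).

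- Placebo response: Φ((15 − 20)/20) = Φ(−0.25) = 0.40.
- Active response: Φ((32 − 20)/20) = Φ(0.60) = 0.73.
- The difference is 0.325 and the mean rate 0.563. Pooled SE = √(2 × 0.563 × 0.437/30) = 0.128. Unpooled SE = √((0.240 + 0.199)/30) = 0.121.
- Power = Φ((0.325 − 1.96 × 0.128)/0.121) = about 73%.

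**3. Why the gain differs by outcome.** Write the month-3 score as a constant plus β × baseline plus error. Remission depends on the month-3 score, which has slope β in baseline. Response depends on the fall, which has slope 1 − β. Adjustment therefore cannot help remission when β = 0, or response when β = 1.

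**4. Simulated power.** 4,000 trials per row, 30 per arm, SD of change 20, falls 15 vs 32, scores limited to 0–100, baseline from 27 up. Pearson chi-square is compared with the logistic score test adjusted for baseline. Baseline SD and β are assumptions; the baseline mean (55 to 57) lies in the plan's expected range.

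| Baseline SD | β | Correlation | Remission: chi-square → adjusted | Response: chi-square → adjusted |
|---|---|---|---|---|
| 11.6 | 0.3 | 0.19 | 72.4 → 73.7 | 74.5 → 78.2 |
| 11.6 | 0.5 | 0.29 | 66.8 → 70.2 | 73.9 → 76.3 |
| 11.6 | 0.7 | 0.38 | 63.0 → 67.7 | 74.0 → 74.6 |
| 15.5 | 0.3 | 0.27 | 75.8 → 77.4 | 73.0 → 82.1 |
| 15.5 | 0.5 | 0.39 | 66.2 → 69.9 | 74.8 → 79.1 |
| 15.5 | 0.7 | 0.49 | 58.0 → 64.8 | 73.1 → 74.6 |

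- The central rows (β = 0.5) gain about 2 to 4 points. In the 0.39-correlation row this is worth roughly 10% more patients.
- With an intermediate baseline, N(55, 14) cut at 27, and β from 0.3 to 0.7, the gain is about 1 to 5 points per outcome. Repeat runs put the top of that range near 6.
- At the extremes (β = 0 or 1), one outcome gains nothing. The other gains up to 18.7 points (response, β = 0) or 10.5 (remission, β = 1; 12.4 with falls of 15 vs 35). The lowest change anywhere was −0.3 points, within simulation error.
- Under no treatment effect, with the N(55, 14) baseline and β from 0.3 to 0.7, the adjusted score test rejected in 4.6 to 5.6% of trials. A likelihood-ratio test ran at 5.2 to 6.6%, so the choice of test matters at this size.

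**5. Chance imbalance.** With N(55, 14) cut at 27, the baseline SD is about 13.2, so the arm difference in mean baseline has SD 13.2 × √(2/30) = 3.4 points. An imbalance of that size shifts the remission difference by 1.8 to 3.6 percentage points and the response difference by 1.7 to 4.3, in opposite directions. The sampling SDs are 11 to 12 points, so imbalance explains 2 to 13% of the variance: (1.8/12)² = 2% and (4.3/12)² = 13%. Across trials the two estimated differences stay positively correlated, at 0.41 to 0.49.

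**The case against.** The strongest reply is that this is a preference about efficiency. Chi-square on randomised arms is valid, it estimates the plain difference in proportions, and it is used here for secondary outcomes. The trial is powered on the mean change, which is already adjusted. The simulated remission power of 58 to 76% in the table is for a 17-point mean shift. That shift corresponds to a remission difference of about 25 to 29 points, which the plan does not claim to detect. All of this stands.

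A reader might infer that power is being thrown away, or that baseline imbalance makes remission and response hard to interpret together. The documents do not support either reading. The likely gain is a few points and rests on inputs the plan does not give. The opposing push from baseline is small against sampling error, and the two estimates still tend to move together. The patient entering at 27 is also an edge case, given expected scores of 50 to 60.

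The remaining objection is that logistic fitting is fragile when events are few. The cited budesonide trial had 7% placebo remission, which is about 2 of 30. This is a fair caution. It supports a named fallback and a careful choice of test, but it is not a reason to leave baseline out: the score test held close to 5%.

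**Conclusion.** The point holds as a cheap improvement. Section 9.4.3 leaves out a covariate that is already collected, is used in the primary model, and is linked by definition to both outcomes. The plan gives no reason for the omission.

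The expected gain at 30 per arm is about 1 to 5 power points per outcome, and 2 to 4 in central scenarios. It may be close to zero for one outcome. This rests on an assumed baseline SD of about 14 and a slope of 0.3 to 0.7, together with the plan's SD of 20 and falls of 15 vs 32. A wider baseline spread or a slope near 0 or 1 would raise the gain for one outcome and remove it for the other.

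The planned tests are not wrong, and the stated power for a 40-point remission difference needs no correction.

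**What to change.** In section 9.4.3, for both remission and response:

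- Pre-specify logistic regression on treatment arm and continuous baseline EEsAI.
- Name the test in advance: the score test for treatment, or a re-randomisation test. Avoid relying on the likelihood-ratio test at this sample size.
- Report the standardised (marginal) risk difference with a 95% CI, so that the estimand remains the difference in proportions.
- Keep chi-square as the supportive analysis, and name it as the fallback if events are too sparse for the model to be fitted. State that rule before unblinding.

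The cost is a change of SAP wording, a little more programming, and some small-sample care over the test and standard error. No extra data, visits or patients are needed.
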